2.1.1.4 Post-baseline definition

Post-baseline measurements are defined as the assessments after the first dose of study treatment. When change from baseline of raw or log-transformed data is of interest, the following formula will be used to calculate the change from baseline, provided, both baseline and post-baseline values are available:

Change from baseline = post-baseline value – baseline value.

2.1.1.5 Maximum tolerated dose in DBPCFC

Maximum tolerated dose (MTD) is defined as the maximum tolerated single dose without any dose limiting symptoms in peanut challenge part. If the MTD at any visit is 0mg, it will be imputed as 0.3 mg and reported as “< 1 mg.”

2.2 Analysis sets

The Randomized Analysis Set (RAS) consists of all randomized participants, regardless of whether or not they receive a dose of study drug. Participants will be analyzed according to the treatment they are assigned to.

The Full Analysis Set (FAS) comprises all participants who received at least one dose of study treatment. According to the intent to treat principle, participants will be analyzed according to the treatment they have been assigned to during the randomization procedure. Mis-randomized patients (mis-randomized in IRT) will be excluded. Mis-randomized patients are defined as cases where IRT contacts were made by the site either prematurely or inappropriately prior to confirmation of the patient's final randomization eligibility and no study medication was administered to the patient. FAS will be used for all efficacy variables, unless otherwise stated.

The Safety Set (SAF) includes all participants who received at least one dose of study treatment whether or not being randomized. Participants will be analyzed according to the treatment they received, where treatment received is defined as the randomized/assigned treatment if the participant took at least one dose of that treatment or the first treatment received if the randomized/assigned treatment was never received. The safety set will be used in the analysis of all safety variables.

[REDACTED]

[REDACTED]

2.2.1 Subgroups of interest

Subgroup analyses will be performed for primary endpoint and selected secondary endpoints using the same models mentioned in Section 2.6 and Section 2.7 but with additional model terms for the subgroup (if not already included in the model) and subgroup-by-treatment interaction terms. Due to the reduced number of participants who completed the study, models for subgroup analyses may fail to converge after dropping factors, then only descriptive subgroup analyses will be provided instead. The subgroup variables are listed below:

- By age group (12 – 17 years, 18 – 55 years)
- By total IgE at screening (<350 IU/ mL; ≥350 IU/ mL)
- By age group and total IgE at screening
- By maximum tolerated dose of allergen at screening OFC (< 30 mg; ≥ 30 mg)
- By allergy status (mono- vs poly-sensitized participants)

Mono-sensitized participants are only sensitized to peanut protein. Poly-sensitized participants are sensitized to peanut protein and at least one of the other proteins in the panel. Poly-sensitization is defined as sIgE ≥ 0.35 kUA/L for a food allergen in the panel other than peanut and confirmed in the medical history.

The following subgroup analysis may be conducted to evaluate potential impact of temporary halt on primary and key secondary efficacy endpoints, if participants who have not reached

Week 12 upon receiving the notification of temporary halt (Date of issuing temporary halt notification : 05 Apr 2023) have a dropout rate greater than or equal to 25%:

- By Week 12 completion date (or date of study discontinuation if study discontinuation occurred prior to Week 12) before or after the notification of the halt.

In addition, subgroup analyses by age (12-17 years and 18-55 years) for selected safety endpoints, [REDACTED] will also be provided.

2.3 Patient disposition, demographics, and other baseline characteristics

2.3.1 Patient disposition

For each study epoch (i.e., screening, treatment phase and post treatment follow-up), the overall number of participants who entered, completed and discontinued that phase will be summarized including the primary reasons for discontinuation of that phase.

The number of participants who completed the 12-week and 52-week study treatment and who discontinued prematurely will be shown including the reasons for discontinuation of treatment.

Number of participants with protocol deviations will be summarized by category and deviation.

2.3.2 Demographics and other baseline characteristics

Demographic and other baseline data including disease characteristics will be summarized descriptively by treatment group for the RAS.

Demographics

- Age
- Age group (12-17 years and 18-55 years)
- Sex
- Race
- Ethnicity
- Region [Japan; US and Canada (North America); Australia; Denmark, France, Germany, Italy, Spain, the Netherlands (EU)]
- Weight
- Height
- Body Mass Index – calculated as $\text{weight (kg)} / (\text{height (m)})^2$
- BMI group (< 25 , $25 - < 30$, ≥ 30 kg/ m²)

Baseline characteristics

- Peanut sIgE
- Peanut specific IgG4
- SPT mean wheal diameter
- MTD (maximum tolerated dose) of peanut protein at screening DBPCFC ($<1 < 1$, 1, 3, 10, 30 mg)

- Poly-allergic to food
- History of anaphylactic reaction to food (Yes, No)
- Number of Use of Epinephrine auto-injector in the last two years
- Duration of peanut allergy (months since peanut allergy diagnosis)
- History of desensitization therapy to peanut allergy (Yes, No)

Categorical data will be presented as frequencies and percentages. For continuous data, mean (geometric mean for non-normal distributed variables), standard deviation, median, minimum, and maximum will be presented.

Relevant medical histories and current medical conditions at baseline will be summarized by system organ class and preferred term, by treatment group.

2.4 Treatments (study treatment, rescue medication, concomitant therapies, compliance)

2.4.1 Study treatment / compliance

The duration of exposure in weeks to each treatment group will be summarized using descriptive statistics.

Duration of exposure to study treatment will be calculated as the number of weeks between the first dose date and the last dose date exposed to that treatment over the specified period (Duration of exposure = (date of last known study treatment – date of first known study treatment + 28)/7).

In addition, the number of doses, total cumulative dose and number of missed doses will be presented. Categorical data will be summarized as frequencies and percentages. For continuous data, mean, standard deviation, median, 25th and 75th percentiles, minimum and maximum will be presented.

2.4.2 Prior, concomitant and post therapies

Prior medications are defined as treatment taken and stopped prior to first dose or study treatment. Prior medications will be summarized by Anatomical Therapeutic Chemical (ATC) code, preferred term and treatment group on RAN set, separately for peanut allergy treatment (other than the ones taken during screening DBPCFC) and non-peanut allergy treatment (including ones taken during screening DBPCFC). For peanut allergy treatment, reason for discontinuation will be summarized as well.

Concomitant medications are defined as any medication given at least once between the day of first dose of study treatment and the date of the last study visit. Concomitant medications will be summarized by ATC code, preferred term and treatment group for safety set.

Rescue medications will be summarized by ATC code, preferred term and treatment group for safety set.

Use of epinephrine during and outside of OFC will be summarized separately. Epinephrine used during the OFC are reported by the Investigator, on the concomitant medication eCRF page

after choosing Yes to the question on OFC signs and symptoms eCRF page: Was any treatment provided for these sign/symptoms?

Significant prior and concomitant surgeries and procedures will be summarized by primary system organ class and MedDRA preferred term.

2.5 Analysis supporting primary objective(s)

This section will describe the statistical analysis of the primary estimand. Details of the hypothesis testing strategy including primary and key secondary endpoints to handle multiplicity are provided in [Section 2.6.2](#).

2.5.1 Primary endpoint(s)

Definition of primary estimand is provided in [Section 1.2.1](#).

2.5.2 Statistical hypothesis, model, and method of analysis

The trial will be considered positive, if at least one of the two ligelizumab doses demonstrates a statistically significant result in comparing the proportion of responders as described below. The two doses will be tested in parallel for 12 weeks treatment on the primary endpoint.

Let p_j denote the responder rate for treatment regimens j , $j=0, 1$ or 2 where

- 0 corresponds to placebo
- 1 corresponds to ligelizumab 120 mg treated for 12 weeks
- 2 corresponds to ligelizumab 240 mg treated for 12 weeks

Responder rate is defined as the proportion of participants tolerating a single dose of ≥ 600 mg (1044 mg cumulative tolerated dose) of peanut protein without dose-limiting symptoms during the DBPCFC conducted at Week 12. For participants with treatment discontinuation or missing more than 1 doses of study drug prior to Week 12 due to reasons other than operational complications caused by public health emergency, they will be considered non-responders.

The following hypotheses will be tested:

H_0 120 RR600 : $p_1 / (1 - p_1) \leq p_0 / (1 - p_0)$ versus H_A 120 RR600 : $p_1 / (1 - p_1) > p_0 / (1 - p_0)$

H_0 240 RR600 : $p_2 / (1 - p_2) \leq p_0 / (1 - p_0)$, H_A 240 RR600 : $p_2 / (1 - p_2) > p_0 / (1 - p_0)$

H_0 120 RR600 : ligelizumab 120mg is not superior to placebo with respect to the responder rate at a level of 600 mg peanut protein (1044 mg cumulative tolerated dose) without dose-limiting symptoms at Week 12

H_0 240 RR600 : ligelizumab 240mg is not superior to placebo with respect to the responder rate at a level of 600 mg peanut protein (cumulative tolerated dose 1044 mg) without dose-limiting symptoms at Week 12

The primary endpoint will be analyzed based on a logistic regression model, including treatment, age subgroup (12 – 17 years, 18 – 55 years), region as fixed class effects, as well as log-transformed total IgE at screening and log-transformed MTD (Maximum Tolerated Dose) at screening DBPCFC as covariates. P-value will be generated with a likelihood ratio test. Odds

ratio and 95% profile likelihood confidence intervals (CI) will be presented comparing each ligelizumab dose to placebo with respect to the proportions of responders.

The detailed testing strategy for primary and key secondary endpoints is provided in [Section 2.6.2](#).

2.5.3 Handling of missing values not related to intercurrent event

Handling of intercurrent events associated with key secondary objectives are described in the [Section 1.2.1](#). Missing data not related to intercurrent events will be imputed for primary endpoint using multiple imputation under the missing at random (MAR) assumption. Details of the imputation method are mentioned in the [Section 5.4.1](#).

2.5.4 Supplementary analyses

Two supplementary analyses will be performed for the primary endpoint.

Marginal Standardization

The first supplementary estimand is the same as for the primary estimand except that the summary measure is the risk difference for marginal proportions of responders. The risk difference will be derived from the predicted risks for every patient as if they had received each treatment using a logistic regression model ([Ge et al 2011](#)). The model will include the same terms as in the primary analysis. The estimated treatment group risks, risk difference and 95% CI will be presented. Details are provided in [Section 5.4.1](#).

Kaplan-Meier plot

A Kaplan-Meier plot will show the probability of experiencing a dose-limiting symptom during dose escalation of DBPCFC at Week 12 by treatment group. The dose of peanut protein at which dose-limiting symptom occurs during the DBPCFC at Week 12 will be treated as the time variable. There will be two separate plots showing those who completed DBPCFC at Week 12: the first will show the results for the overall population; the second will be stratified by the highest tolerated dose of peanut protein at baseline (< 30 mg or >= 30mg). Participants' maximum tolerated dose may be censored if they:

- tolerated 3000mg of peanut protein; or
- completed a certain level of challenge dose without experiencing dose-limiting-symptoms and chose to stop the DBPCFC before beginning or finishing a higher challenge dose (for example, due to the taste of the challenge material).

2.6 Analysis supporting secondary objectives

This section describes the analyses of key secondary and other secondary endpoints. The details of the analyses are described below.

2.6.1 Key secondary endpoint(s)

Definition of key secondary endpoints is provided in [Section 1.2.2](#).

The other secondary endpoints and corresponding analyses are defined in the [Section 2.6.5](#) below.

2.6.2 Statistical hypothesis, model, and method of analysis

Key secondary endpoint analyses

The key secondary null hypotheses are as defined below. The familywise type I error rate will be controlled at the one-sided 0.025 level across the primary and key secondary null hypotheses in a closed testing procedure ([Bretz et al 2009](#)).

$H_{0\ 120\ RR1000}$: ligelizumab 120 mg is not superior to placebo with respect to the responder rate at a level of 1000 mg peanut protein (cumulative tolerated dose 2044 mg) at Week 12

$H_{0\ 240\ RR1000}$: ligelizumab 240 mg is not superior to placebo with respect to the responder rate at a level of 1000 mg peanut protein (cumulative tolerated dose 2044 mg) at Week 12

$H_{0\ 120\ RR3000}$: ligelizumab 120 mg is not superior to placebo with respect to the responder rate at a level of 3000 mg peanut protein (cumulative tolerated dose 5044 mg) at Week 12

$H_{0\ 240\ RR3000}$: ligelizumab 240 mg is not superior to placebo with respect to the responder rate at a level of 3000 mg peanut protein (cumulative tolerated dose 5044 mg) at Week 12

$H_{0\ 120\ severity}$: ligelizumab 120 mg is not superior to placebo with respect to the odds of developing less severe level of symptoms evaluated by maximum severity of symptoms at any challenge dose of peanut protein up to and including 1000 mg during the DBPCFC conducted at Week 12

$H_{0\ 240\ severity}$: ligelizumab 240 mg is not superior to placebo with respect to the odds of developing less severe level of symptoms evaluated by maximum severity of symptoms at any challenge dose of peanut protein up to and including 1000 mg during the DBPCFC conducted at Week 12

[figure not shown]
The following secondary hypotheses will be used to evaluate onset of action of ligelizumab (8 weeks of placebo + 4 weeks of ligelizumab treatment):

$H_{0\ 120\ wk4\ RR1000}$: ligelizumab 120 mg (8 weeks of placebo + 4 weeks of ligelizumab treatment) is not superior to placebo with respect to the responder rate at a level of 1000 mg peanut protein (cumulative tolerated dose 2044 mg) at Week 12

$H_{0\ 240\ wk4\ RR1000}$: ligelizumab 240 mg (8 weeks of placebo + 4 weeks of ligelizumab treatment) is not superior to placebo with respect to the responder rate at a level of 1000 mg peanut protein (cumulative tolerated dose 2044 mg) at Week 12

The graphical approach of [Bretz et al 2009](#) for sequentially rejecting testing procedures is used to illustrate the testing strategy in [Figure 2-1](#) below.

Figure 2-1 Testing strategy

- The hypotheses will be tested in two branches constituting ligelizumab 120 mg versus placebo (left branch) and ligelizumab 240 mg versus placebo (right branch). Initially, the full alpha level of 0.025 (one-sided) is equally split across the primary hypotheses for the two branches.
- Once this first primary null hypothesis H₀ 120 RR600 or H₀ 240 RR600 for a dose has been rejected at the initial alpha level of 0.0125 (one-sided), the alpha will be fully distributed to H₀ 120 RR1000 or H₀ 240 RR1000 for the same dose.
- If H₀ 120 RR1000 or H₀ 240 RR1000 is rejected for a dose, then 50% of its local significance level is reassigned to the primary null hypothesis for the other dose, and 50% of its local significance level is reassigned to H₀ 120 RR3000 or H₀ 240 RR3000 for the same dose.
- If H₀ 120 RR3000 or H₀ 240 RR3000 is rejected for a dose, then 50% of its local significance level is reassigned to the primary null hypothesis for the other dose, and 50% of its local significance level is reassigned to H₀ 120 severity or H₀ 240 severity for the same dose.
- If H₀ 120 severity or H₀ 240 severity is rejected for a dose, (100-ε)% of its local significance level is reassigned to the primary null hypothesis for the other dose. ε is set to a very small number in practice, e.g., 10⁻¹⁰. The dotted dashed edges with a weight of ε indicate the local significance level will only be reassigned to H₀ 120 wk4 RR1000 or H₀ 240 wk4 RR1000, once both H₀ 120 severity and H₀ 240 severity are rejected.
- If H₀ 120 wk4 RR1000 or H₀ 240 wk4 RR1000 is rejected for a dose, 100% of its local significance level is reassigned to the primary null hypotheses for the other dose.

The proportion of responders for the endpoints as stated below will be analyzed using a logistic regression model in a similar fashion as the primary estimand (see [Section 5.4.1](#) for details).

- Responder status defined as tolerating a single dose of 1000 mg (2044 mg cumulative tolerated dose) peanut protein without dose-limiting symptoms as Week 12.
- Responder status defined as tolerating a single dose of 3000 mg (5044 mg cumulative tolerated dose) peanut protein without dose-limiting symptoms at Week 12.

- Responder status defined as participants tolerating a single dose of ≥ 1000 mg (2044 mg cumulative tolerated dose) peanut protein without dose-limiting symptoms at Week 12 (8 weeks of placebo + 4 weeks of ligelizumab treatment vs. 12 weeks of placebo).

The odds of developing less severe level of symptoms for the endpoint, defined as maximum severity of symptoms occurring at any challenge dose of peanut protein up to and including 1000 mg during the DBPCFC conducted at Week 12, will be analyzed with a proportional odds model, including treatment, age subgroup (6-11 years, 12-17 years, 18-55 years), region as fixed class effects and log-transformed baseline total IgE at screening as a covariate.

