## **12.5 Analysis supporting secondary objectives**

### **12.5.1 Efficacy and/or Pharmacodynamic endpoint(s)**

#### **Key secondary endpoints**

Definitions of secondary estimands for key secondary objectives are provided in [Section 2.2](#).

The key secondary efficacy endpoints are:

- Responder status defined as tolerating a single dose of  $\geq 1000$  mg (2044 mg cumulative tolerated dose) peanut protein without dose-limiting symptoms at Week 12. The proportion of responders will be analyzed using the logistic regression model in a similar fashion as the primary estimand. Intercurrent events and missing data will be handled following the same principle as for the primary estimand.
- Responder status defined as tolerating a single dose of 3000 mg (5044 mg cumulative tolerated dose) peanut protein without dose-limiting symptoms at Week 12. The proportion of responders will be analyzed using the logistic regression model in a similar fashion as the primary estimand. Intercurrent events and missing data will be handled following the same principle as for the primary estimand.
- Maximum severity of symptoms occurring at any challenge dose of peanut protein up to and including 1000 mg during the DBPCFC conducted at Week 12. Symptom severity will be categorized as 4 levels: None, Mild, Moderate, Severe. The odds of developing less severe level of symptoms will be analyzed with a proportional odds model, including treatment, age group (6 – 11 years, 12 – 17 years, 18 - 55 years), region as fixed class effects and log-transformed total IgE at Screening Visit 1 as a covariate. Missing data at Week 12 corresponding to the intercurrent events of category 1 as described in [Section 2.2.3](#) will be multiply imputed in line with the treatment policy strategy. For participants in the active treatment arms, missing data will be imputed based on placebo data. For participants in the placebo arm, missing data will be imputed based on the observed placebo arm data under a missing at random (MAR) assumption (treatment policy strategy). Other intercurrent events and missing data will be handled with a similar hypothetical strategy as for the primary estimand.

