Added information about prior medications, concomitant medications, and epinephrine use. Replaced summaries by ATC classification by primary system organ class and MedDRA preferred term.	Section 2.4.2
Added log-transformed MTD (Maximum Tolerated Dose) at screening DBPCFC as covariate in logistic regression model. Added P-value will be generated with a likelihood ratio test.	Section 2.5.2
Removed tipping point analyses as missing data due to intercurrent events will be handled with relative conservative strategy (i.e., composite variable strategy)	Section 2.5.3
Added Kaplan-Meier plot and modified marginal standardization analysis.	Section 2.5.4
Maximum tolerated dose analyses and skin prick test described in more detail.	Section 2.6.4
Pooling periods for safety analyses described elsewhere (Section 2.1.1.1).	Section 2.7
Added details on treatment-emergent adverse events.	Section 2.7.1
Added exposure-adjusted incidence rate.	Section 2.7.1.1
Added details for summarizing injection site reactions.	Section 2.7.1.2
Imputation methods described for values that are abnormal or outside the level of quantification.	Section 2.7.3 and Section 2.8
Details on ECG parameters provided.	Section 2.7.4.1
[REDACTED]	[REDACTED]
IgE levels specified as at screening.	Section 2.9
Age groups and scoring of PRO instruments clarified, including SF-6Dv2.	Section 2.10.1
Analysis for PRO scores described.	Section 2.10.1.1
[REDACTED]	[REDACTED]
Power calculations updated using PASS Version 11. Paragraph on consistency trend across age groups removed.	Section 3.1
Sentence about potentially increasing sample size for covid impact was removed. Power table for children 6-11 removed.	Section 3.2
Table on precision levels for safety incidence rate per age group removed.	Section 3.2.1
Changes to protocol specified analyses noted.	Section 4
Details for multiple imputation added, for maximum tolerated dose, binary endpoints involving logistic regression, and marginal standardization. Tipping point analysis for primary estimand removed.	Section 5.4.1
For maximum severity of symptoms, covariates were specified and details on imputation strategy added.	Section 5.4.2
IgE specified as being measured at screening.	Section 5.4.2.1

11 Sep 2023	Before database lock	Clarification of analyses	Specified calculation of negative control for skin prick test mean diameters.	Section 2.6.4
			Removed SF-36 output from Table 2-2 and specified missing data approach for additional analysis	Section 2.13

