2.6.4 Other secondary endpoint analyses

Secondary endpoints which are not part of the testing strategy include:

- Proportion of participants tolerating a single dose of ≥ 1000 mg (2044 mg cumulative tolerated dose) of peanut protein without dose-limiting symptoms during DBPCFC conducted at Week 52

Number and percentage of responders at Week 52 will be summarized by treatment group in overall population. Number and percentage of responders at Week 52 may also be summarized by treatment group in the subset of responders at Week 12. Missing data of DBPCFC at Week 52 will not be imputed. The summary statistics will be provided for observed data.

- Change in maximum tolerated dose (MTD) of peanut protein without dose-limiting symptoms during the DBPCFC at Week 52 compared to Week 12

MTD at Week 52 along with changes from baseline and changes from Week 12 will be summarized descriptively. Missing data will not be imputed. The summary statistics will be provided for observed data.

- Change from baseline in MTD of peanut protein without dose-limiting symptoms during the DBPCFC at Week 12

An analysis of covariance (ANCOVA) model of change from baseline in log transformed MTD at Week 12 DBPCFC will be fit with terms for treatment group, age subgroup (12-17 years, 18-55 years), log-transformed total IgE at Screening Visit 1, region, and log-transformed MTD at baseline. Missing MTD at Week 12 values due to intercurrent events will be imputed by screening MTD, and other missing data will be multiply imputed under MAR assumption. If model assumptions of homoscedasticity and normality are not met, then the Wilcoxon rank-sum test may be performed.

- Change from baseline in peanut-specific IgE and IgG4 at Week 12, Week 16 and Week 52

Summary statistics, including geometric means and standard deviations, will be presented for peanut-specific IgE and IgG4 along with changes from baseline by time point and treatment group. The summary statistics will be provided for observed data. Change from baseline in log-

transformed levels of peanut specific-IgE and peanut specific-IgG4 at Week 12 and Week 16 will be analyzed using an ANCOVA model with terms for treatment group, age group, region, log-transformed total IgE at Screening Visit 1, and log-transformed baseline peanut specific-IgE or peanut specific-IgG4. Values below the LLOQ or above the ULOQ will be imputed as half the LLOQ or as the ULOQ, respectively.

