3.2.1 Precision for adverse events

Table 3-3 Precision levels (95% CI) for sensitivity of safety incidence rate for overall population

Event rate (proportion of participants with an event)	Number of participants	95% CI
0%	486	(0%, 0.8%)
1%	486	(0.3%, 2.3%)
2%	486	(1%, 3.7%)
0%	211	(0%, 1.7%)
1%	211	(0.1%, 3.5%)
2%	211	(0.6%, 4.9%)

4 Change to protocol specified analyses

On 31 March 2023, Novartis made a strategic decision to close recruitment in study CQGE031G12301 and terminate the study early. As a result, there are several changes to the specified analyses in the protocol, namely:

- Instead of 486 participants, the sample size is 211.

- There will be no recruitment of children under age 12, and the age-groups of interest are now 12-17 and 18-55.
- For participants who have reached Screening Visit 2 Part 1 and not completed Week 52 visit at the time of halt recruitment will need to complete Screening Visit 2 Part 2 to determine eligibility. If they are eligible, they will either continue treatment and perform assessments until Week 12 Part 2 or will stop treatment at the next scheduled visit if they have already completed Week 12 Part 2. This leads to limited number of participants reaching Week 52. Hence, non-inferiority test for sustainability of treatment effect at Week 52 compared to Week 12 is removed.
- Week 52 interim analysis will not be conducted.

There are also some changes made to simplify the analyses:

- Since the number of COVID-19 related intercurrent events is expected to be minimal, references to COVID-19 related intercurrent events were removed.
- Handling of intercurrent events for the secondary estimands were changed to be consistent with the primary estimand strategy.
- The two-dimensional tipping point analysis for the primary estimand was removed.

In analysis for primary estimand and secondary estimands(1, 2 and 4), log-transformed MTD at screening DBPCFC was added as covariate in logistic regression models.

The protocol mentions the summary measure of supplementary estimand is relative risk generated with a marginal standardization method. In SAP, relative risk is changed to risk difference to facilitate clinical interpretation.

5 Appendix

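### On the visible text the maximum-severity model leaves out log screening MTD, which the SAP's other modelled Week 12 challenge endpoints include, and it still lists the unrecruited 6–11 age class

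*SAP*

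**What the plan says.** - **Severity model.** SAP Section 2.6.2 says the endpoint "will be analyzed with a proportional odds model, including treatment, age subgroup (6-11 years, 12-17 years, 18-55 years), region as fixed class effects". The list of terms ends with "region as fixed class effects and log-transformed baseline total IgE at screening as a covariate", so log total IgE is the only continuous covariate. Protocol Section 12.5.1 has the same terms: "The odds of developing less severe level of symptoms will be analyzed with a proportional odds model, including treatment, age group" in three classes, region and log total IgE.
- **Primary model.** SAP Section 2.5.2 uses two age classes (12–17 and 18–55) and adjusts for "log-transformed total IgE at screening and log-transformed MTD (Maximum Tolerated Dose) at screening DBPCFC as covariates".
- **Other key secondary endpoints.** Section 2.6.2 has the 1000 mg, 3000 mg and 4-week 1000 mg responder endpoints follow the primary logistic model. Section 4 declares the change: "In analysis for primary estimand and secondary estimands(1, 2 and 4), log-transformed MTD at screening DBPCFC was added as covariate in logistic regression models". Estimand 3, severity, is not in that list.
- **Week 12 change in MTD.** The ANCOVA in Section 2.6.4 includes "log-transformed total IgE at Screening Visit 1, region, and log-transformed MTD at baseline", with two age classes.
- **Document history.** For Section 2.5.2: "Added log-transformed MTD (Maximum Tolerated Dose) at screening DBPCFC as covariate in logistic regression model". For Section 5.4.2: "For maximum severity of symptoms, covariates were specified and details on imputation strategy added". The text of Section 5.4.2 is redacted. The visible rows show no entry for Section 2.6.2.
- **Recruitment.** Sections 1.1 and 4 say that only adolescents and adults were recruited, 211 in total.

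**The concern.** Severity comes from the same food challenge as the responder endpoints, yet on the visible text it is the only one of the modelled Week 12 challenge endpoints without screening MTD. The leftover 6–11 class suggests that the sentence was carried over from the protocol when the other models were revised.

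Power is what is at stake. The severity hypotheses are part of the alpha-controlled procedure, and under the graphical procedure in Section 2.6.2 the 4-week hypotheses receive alpha only when both severity nulls are rejected. The trial has also shrunk from 486 to 211 participants, while Table 3-2 still gives severity power only at 108 per dose and 54 on placebo. If screening MTD predicts severity, leaving it out gives up power at the two severity tests and at the step that opens the 4-week tests.

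**Working it through.** **1. Model terms side by side**

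| Week 12 challenge endpoint | Age classes | Log IgE | Log screening MTD |
|---|---|---|---|
| Tolerates 600 mg (primary) | 2 | yes | yes |
| Tolerates 1000 mg; 3000 mg; 1000 mg after 4 weeks | as primary | yes | yes |
| Change in MTD | 2 | yes | yes (the outcome's own baseline) |
| Maximum severity | 3, one empty | yes | no |

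**2. The plan's own power figures**

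Exact enumeration of the one-sided Fisher test at 0.0125 gives 96.5% for 68% vs 17% at 46 vs 23 (Table 3-1: 96%) and 85.8% for 59.5% vs 17% (Table 3-1: 86%). For severity at 108 vs 54, a tie-corrected Wilcoxon simulation on the Table 3-2 margins gives 99.96% to 99.99% at local levels from 0.003125 to 0.0125 (Table 3-2: above 99.9%). At 46 vs 23, for which the SAP gives no severity figure, the same unadjusted test has 94.8%, 90.9% and 85.5% power at 0.0125, 0.00625 and 0.003125.

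**3. Level at the severity tests**

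Each dose starts with 0.0125. Once both doses have cleared the 600, 1000 and 3000 mg hypotheses, all 0.025 has moved to the two severity nodes, and by symmetry each holds 0.025 / 2 = 0.0125. When one is rejected, the other is tested at about 0.025.

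**4. Simulation of the severity model**

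From the documents:
- 46/46/23 participants (SAP Section 3.1).
- None/Mild/Moderate/Severe 38/32/25/5% on ligelizumab and 2/28/59/11% on placebo (Table 3-2).
- Screening MTD of 0.3 (for below 1), 1, 3, 10 or 30 mg (Sections 2.1.1.5 and 2.3.2).
- Four regions (Section 2.3.2).

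Assumed:
- Equal MTD shares, region shares 10/55/10/25%, a 50/50 age split and IgE not prognostic.
- A latent normal severity score with correlation ρ to log MTD, cut to the Table 3-2 margins.
- The likelihood ratio test that Section 2.5.2 names for the primary endpoint; Section 2.6.2 names no test for severity.

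The statistic is z = sign(β) × √(2(ℓ₁ − ℓ₀)), where β is the estimated treatment log odds ratio (positive for less severe symptoms) and ℓ₁ and ℓ₀ are the maximised log-likelihoods with and without that dose's effect. The null is rejected when z > 2.241, the 98.75th normal percentile. There were 20,000 trials per setting and no failed fits. Results were not conditioned on earlier rejections. Each cell shows without / with log MTD.

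| ρ | Power per dose, % | Change, points | Both nulls rejected, % | Median SE of log OR | Median OR |
|---|---|---|---|---|---|
| 0 | 93.58 / 93.46 | −0.1 | 93.8 / 93.7 | 0.507 / 0.510 | 5.82 / 5.91 |
| 0.15 | 93.59 / 93.92 | +0.3 | 93.7 / 94.0 | 0.507 / 0.512 | 5.83 / 6.03 |
| 0.3 | 93.55 / 95.17 | +1.6 | 93.7 / 95.4 | 0.507 / 0.517 | 5.81 / 6.46 |
| 0.5 | 93.50 / 97.74 | +4.2 | 93.5 / 97.9 | 0.506 / 0.535 | 5.81 / 7.94 |

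The Monte Carlo error of each paired difference is 0.05 to 0.12 points. The chance of rejecting both can exceed the single-test power because the second null is tested at about 0.025. The standard error rises slightly with MTD in the model; power is gained because the odds ratio, now conditional on MTD, moves further from 1.

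**5. Checks**

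- Wald tests give the same pattern: 93.2/93.1, 93.2/93.6, 93.2/94.9 and 93.1/97.6%.
- Type I error of one likelihood ratio test at nominal 1.25% is 1.56/1.61% at ρ = 0 and 1.65/1.74% at ρ = 0.5, so MTD adds at most about 0.1 point.
- Unequal MTD shares (5/10/20/30/35%) give 93.4/95.1% at ρ = 0.3 and 93.1/97.8% at ρ = 0.5. Making IgE prognostic as well (0.3) gives 95.0/96.7% at ρ = 0.3. These checks used 4,000 trials each.
- A separate simulation of 2,000 trials per setting gives 93.3/93.1, 93.4/95.3 and 93.5/97.9% at ρ = 0, 0.3 and 0.5.

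**The case against.** The strongest reply is that Section 5.4.2, which the history says specifies the severity covariates, is redacted and may already include MTD. Redacted text cannot be counted as missing, and because some history rows are also blacked out, the lack of a visible entry for Section 2.6.2 is weak evidence. That limit stands. It does not rescue Section 2.6.2, which states a model without MTD: if Section 5.4.2 lists MTD, the SAP specifies two different models for a confirmatory test.

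The second reply is that naming estimands 1, 2 and 4 looks deliberate, so Sections 2.6.2 and 4 agree with each other and the protocol's covariates were simply kept. That may be so. But the Section 4 sentence concerns logistic regression models and may only follow model type, and no reason is given.

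Third, screening MTD is the natural baseline for tolerated-dose outcomes, whereas for severity the SAP's own baseline is severity at screening, which replaces missing Week 12 values after intercurrent events (Section 1.2.2.3). This has force. MTD is suggested because the SAP already uses it for the same challenge; screening severity was not evaluated here.

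Finally, the gain rests on an unknown correlation, exceeds 2 points only at the largest value tried, and comes with a changed odds ratio. All of that is true, and it is why the point is minor. That the age label is editorial is also conceded.

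**Conclusion.** The concern holds, as a minor efficiency and consistency point. The severity test without MTD is valid and nothing here suggests bias. Adding MTD changes power per dose by between −0.1 and +4.2 points, and the chance of opening the 4-week tests by between −0.1 and +4.4 points (93.5 to 97.9%), for assumed latent correlations from 0 to 0.5. These figures rest on the Table 3-2 margins, 46/46/23 participants, a level of 0.0125 per severity test and the assumed covariate distributions. The cost if MTD is not prognostic is about 0.1 point. The 6–11 class adds no parameter and changes no result, but it is wrong on any reading. Confidence is medium, because the redacted Section 5.4.2 could reduce the MTD part to a matter of alignment.

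**What to change.** In Section 2.6.2, define the severity model as proportional odds with treatment, age subgroup (12–17, 18–55) and region as class effects, and log total IgE and log MTD, both from screening, as covariates. In Section 4, extend the MTD change to estimand 3 and note that the severity odds ratio is then conditional on screening MTD.

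If Section 5.4.2 already lists MTD for severity, only align Sections 2.6.2 and 4 with it. If severity was left out on purpose, give the reason in Section 4 and still correct the age classes.

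The cost is one sentence in Section 2.6.2, one phrase in Section 4 and one extra model term. It should be agreed before the Week 12 unblinding, so that the covariate is not chosen with results in hand.
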